**C. Background and Rationale**

Interscalene brachial plexus block (ISB) is regarded as the standard of care for analgesia after shoulder surgery providing superior analgesia and reducing opioid consumption. ISB can have complications including ipsilateral phrenic nerve block resulting in diaphragmatic paralysis for the duration of the block which can result in temporary ventilatory compromise for patients with reduced respiratory reserve. Nonetheless, the benefits more often outweigh the risks in the appropriate patient population by reducing ventilatory depression associated with significant opioid use after painful upper extremity surgery. Shoulder surgery, previously requiring inpatient admission for pain control, is now commonly performed on an ambulatory basis facilitated by ISB analgesia. The effects of single injection ISB dissipate after several hours unmasking the moderate to severe pain of the surgical insult and require strong opioid analgesia. Efforts to prolong ISB duration by increasing local anesthetic (LA) dose are limited by their pharmacodynamics and narrow therapeutic window.

A broad cross section of surgical patients consistently ranks postoperative pain as their highest concern highlighting the necessity for prolonged and effective postoperative analgesia. Strategies to prolong ISB analgesia include the placement of indwelling perineural catheters to allow for prolonged infusion.

Indwelling catheter techniques can be very effective and provide analgesia for several days but their utility is limited by technical challenges with placement, inherent secondary failure rate, and material cost.

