laryngeal mask airway can be placed for spontaneously breathing patients. Anesthesia will be maintained using the inhalational anesthetic sevoflurane (AbbVie) with an end-tidal concentration of 1.4 - 2%. The surgeon will infiltrate the arthroscopic port insertion sites with 10-40ml total volume of bupivacaine 0.25% (1:200,000 epinephrine) or lidocaine (as determined by the attending physician). Muscle relaxation will be reversed using a combination of neostigmine (0.04mg/kg) and glycopyrrolate (0.007mg/kg) if necessary. Standard anti-emetic prophylaxis with the serotonin antagonist ondansetron (4mg) will be given. For the purpose of this study, patients will not receive additional dexamethasone regardless of group allocation.

Upon arrival to the recovery room, pain (Verbal Response Score  $\geq 4$  or patient request for analgesia) will be treated with intravenous hydromorphone (solely for this study) in 0.2-0.4mg increments every 5 minutes as needed. Postoperative nausea will be treated (as needed) with an additional dose of ondansetron (1mg), droperidol (0.625mg), dimenhydrinate (50mg) or prochlorperazine at the discretion of the attending physician. Capillary blood glucose will also be assessed and recorded for this study. Once oral intake is initiated, patients will receive one of several analgesic preparations as needed: Tylenol #3® (acetaminophen 325 mg/codeine 30 mg/cafeine 15 mg per tablet), or oxycocet (acetaminophen 325 mg/oxycodone HCl 5 mg per tablet), oxycodone 5-10 mg, or hydromorphone 2-4 mg if intolerant to codeine at the discretion of the attending physician. Upon discharge from hospital, patients will receive a prescription for Tylenol #3® as needed, or hydromorphone or oxycocet if intolerant to codeine at the discretion of the attending physician.

After discharge, patients will complete a home pain diary with information that will be collected by research personnel during postoperative telephone calls. Patients will be asked to record the time at which they first experience pain at the surgical site, the time when they first consumed prescribed opioid

analgesics for surgical site pain and when they regained preoperative baseline hand strength.

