Postoperatively patients will be requested to document interval oral analgesic consumption, presence of nausea or vomiting, presence of weakness in the operative arm, and presence of paresthesia (numbness or tingling) in the operative arm. The doses of oral codeine, hydromorphone, or oxycodone consumed by each patient will be converted into equianalgesic doses (oral morphine equivalents). Conversion ratios will be employed according to the general monograph for opioids in the Canadian Pharmacists' Association Compendium of Pharmaceuticals and Specialties (36th ed., 2001) as follows: oral oxycodone: oral morphine sulphate = 1:1.5, oral hydromorphone:oral morphine sulphate = 1:5, and oral codeine: oral morphine sulphate = 6.6:1. The Opioid conversion table has been appended to this protocol.

All patients will be followed-up by telephone on post operative days 1 and 7 (+/- up to 5 days depending on patient availability) to collect the following study data: NRS pain scores, onset of pain and return of the affected hand to normal strength; side effects or complications experienced [(e.g. paresthesia - numbness or tingling, infection at ISB site) in the operative arm, and whether the numbness or tingling was located distal or proximal to the operative site]; and, the quantity, frequency and onset of opioid consumption.

Additional information will not be asked, however if an adverse event (AE) was mentioned during telephone follow-up visits, this will be documented in the AE log and assessed accordingly by the QI.

Additional follow-up telephone visits may be conducted as required in the event of a Serious Adverse Event (SAE) or Adverse Reaction (AR) and will be reported in accordance with the Site Guidance on Safety Reporting document

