**v. Secondary Outcomes**

- Time to first opioid consumption – from end of injection to time to first oral opioid consumption
- Duration of motor block - from end of injection to time of baseline preoperative biceps and hand strength
- Oxygen saturation on room air 1 hour after arrival to recovery room
- Opioid consumption on POD 1 at 12 hours/bed time if patient retires to bed before the 12hr time point), 24 hours and 7 days
- NRS for pain at 12hrs/Bed time (if patient retires to bed before the 12hr time point), 24hours, 7 days
- Blood glucose in recovery room
- Persistent paresthesia in the operative arm at 7 days
- Localized infection at block site at 7 days
- Postoperative nausea

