**vi. Sample size calculation**

Based on our clinical experience with low dose US-ISB (ropivacaine 0.5% 5ml) as well as previously published work, we expect mean sensory block duration of 12 hours with a standard deviation of 4 hours.

Based on the literature, we expect a mean prolongation of block time associated with perineural dexamethasone to be approximately 50% thereby increasing block duration to 18 hours. Defining an equivalency margin of 2 hours, we estimate that 87 patients per group (174 total) will be required to reliably test our hypothesis given  $\alpha=0.05$  and  $\beta=0.9$ . To account for incomplete data or loss to follow-up, the plan is to recruit 90 patients per group (180 total).

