**vii. Statistical analysis**

Demographic data will be summarized and expressed using appropriate measures of central tendency and dispersion for continuous data, means and standard deviations will be provided (medians and interquartile ranges for non-normally distributed data) and for categorical data counts and percentages will be displayed. The primary outcome, time to first sensation of pain at the surgical site, will be compared between the two groups using a two sample equivalence test of means. Secondary outcomes that are time based will also be assessed in the above manner (time to first analgesic request, duration of motor block). Continuous secondary outcomes (opioid consumption, NRS) will be assessed with repeated measures ANOVA while blood glucose will be assessed with the t-test. Categorical outcomes (paresthesia,

infection, nausea) will be compared with the Chi square or Fisher's exact test for the case of low expected cell counts.

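### Time to first opioid (secondary outcome): the analysis section names a different event from the outcome list, and its test of means has no value for a patient who takes no opioid

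*Combined protocol and SAP*

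**What the plan says.** - **Definition.** Section E.v (Secondary Outcomes) runs the clock "from end of injection to time to first oral opioid consumption".
- **Analysis.** Section E.vii (Statistical analysis) states "Secondary outcomes that are time based will also be assessed in the above manner (time to first analgesic request, duration of motor block"). The manner referred to is the equivalence comparison of two means planned for the primary outcome.
- **Recovery room.** Section E.iii (Protocol) says that pain above a threshold "or patient request for analgesia) will be treated with intravenous hydromorphone (solely for this study"). Oral drugs follow: "Once oral intake is initiated, patients will receive one of several analgesic preparations as needed". The discharge opioid is also as needed.
- **Diary.** After discharge, patients note "the time when they first consumed prescribed opioid" analgesics for pain at the operated site.
- **Follow-up.** Patients are "followed-up by telephone on post operative days 1 and 7 (+/- up to 5 days depending on patient availability").
- **Margin.** Section E.vi (Sample size calculation), which concerns sensory block duration, has the only margin: "Defining an equivalency margin of 2 hours".

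No section says how a patient without an opioid time enters the comparison. The increase from 87 to 90 per group covers incomplete data and loss to follow-up. A fully followed patient who took no opioid is neither.

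**The concern.** Two things need settling before the data are analysed.

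First, the event. A request is not consumption, and an analgesic need not be an opioid or a tablet. Two analysts, one working from E.v and one from E.vii, could score the same patient at different times.

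Second, the method. A comparison of means needs a time for everyone. The ordinary way to run it on these data is complete-case, which silently removes patients who never took an opioid. If they are the patients whose relief lasted longest, more are removed from the longer-lasting arm, and the remaining means move closer together. In an equivalence test that error favours the trial's own hypothesis.

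**Working it through.** **Step 1. The plan's own figure.** Inputs from E.vi: SD 4 h, margin 2 h, alpha 0.05 per one-sided test, power 0.90 (printed as beta). With true difference 0:

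n = 2 × [SD × (z0.95 + z0.95) / margin]² = 2 × [4 × (1.645 + 1.645) / 2]² = 86.58, so 87 per group.

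This matches the plan. The sample size is not in question.

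**Step 2. One patient, two scores.** Take a patient who asks for relief in recovery, receives intravenous hydromorphone and swallows a first opioid tablet later. Under the E.vii name the event is the request. Under E.v it is the tablet. If that tablet is taken before discharge, the after-discharge diary alone does not hold it. Hospital doses are recorded (E.viii and the data collection plan), but no section says that the two sources are joined.

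Shift in the arm difference = difference in recovery-opioid rate × gap to first tablet. At equal rates it is 0. At an assumed 5 points and 2 h it is 0.05 × 2 = 0.1 h. The cost is ambiguity more than bias.

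**Step 3. What dropping does to the means.** Assume latent times Normal(18, 4) and Normal(21, 4), a true difference of 3 h, with everyone beyond 24 h taking no opioid (6.7% and 22.7%). The mean among takers is μ − 4 × φ(b)/Φ(b), with b = (24 − μ)/4:

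- μ = 18, b = 1.50: 17.44 h
- μ = 21, b = 0.75: 19.44 h

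The observed difference is 2.00 h instead of 3 h.

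**Step 4. What dropping does to the error rate.** Assumed: 90 per arm, gamma times, means 18 and 20 h, SD 4 h, 2 h margin, two one-sided tests at 5%, never-takers dropped, 20,000 simulated trials. The true difference equals the margin, so equivalence should be declared in 5% of trials.

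| Who takes no opioid | Share per arm | False equivalence |
|---|---|---|
| 5% at random | 5% vs 5% | about 5% |
| A quarter of those beyond 24 h | 2% vs 4% | 7% |
| Half of those beyond 24 h | 4% vs 8% | 11% |
| All beyond 24 h | 8% vs 16% | 28% |

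If the arms are truly equal and one patient is dropped, the chance of showing equivalence is 0.91, the same as with no never-takers.

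**Step 5. Alternatives.** With gamma times and a true 3 h difference:

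| Summary | All beyond 24 h take none | Half do |
|---|---|---|
| Means, never-takers dropped | 2.11 h | 2.64 h |
| Restricted mean, 36 h | 4.27 h | 3.63 h |
| Restricted mean, 48 h | 5.95 h | 4.48 h |
| Kaplan-Meier median difference | 3.00 h | 3.00 h |

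The median recovers the latent difference, and the restricted mean depends on its horizon. The price is precision. The 90% half-width for means is 1.645 × 4 × √(2/90) = 0.98 h; for the difference in medians with 2% never-takers it is about 1.24 h.

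**The case against.** Only E.v defines the outcome. The E.vii phrase is a loose label, and the hydromorphone and diary sentences are treatment and recording instructions. That stands: a reader might infer several rival definitions, but there is one definition and one label that does not fit it.

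The background says that block offset leaves patients "unmasking the moderate to severe pain of the surgical insult and require strong opioid analgesia", so few may go without. That also stands. The 28% needs every patient beyond 24 h to take nothing, and it borrows the mean and SD of another outcome. It is an upper illustration, not a forecast. At the lowest share tried the error is 7%, close to nominal.

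A reader might also infer that the result could turn on one patient and the date of one telephone call, since the day-7 call can fall between day 2 and day 12. That would follow only if an analyst entered last-contact time as though it were an event time. The documents never suggest this.

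Nor do they support extending the point to motor block duration, for which no event-free calculation has been made, or replacing the oral-only definition with one covering every route, which would be a preference.

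The objection does not remove the mismatch in names, the absence of a rule for a patient with no event, or the direction of the bias when never-takers are the longest-relief patients.

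**Conclusion.** The point holds and is minor. E.vii misnames the outcome that E.v defines, and it applies a test that cannot use a patient without an event. Dropping those patients does no harm if never-taking is unrelated to time. If it marks long relief, false equivalence rises from 5% to about 7% to 28% over the shares tried. That range rests on assumed shares and on a mean, SD and margin stated for sensory block duration; the documents give no event-free rate.

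It is tempting to read this as a flaw in the trial's main conclusion. It is not: the primary outcome is a different event, and its sample size reproduces.

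**What to change.** 1. **One definition.** In E.vii use the E.v name and definition. State that in-hospital oral doses come from the recovery and day-surgery records and later doses from the diary.
2. **A method that keeps every patient.** In E.vii replace the test of means for this outcome with a Kaplan-Meier analysis, censoring event-free patients at last contact. Report the median in each arm, the difference in medians with a 90% confidence interval, and the proportion opioid-free at a time fixed in advance. A restricted mean at a prespecified horizon can serve as a sensitivity analysis.
3. **No equivalence claim here.** Report an estimate with its interval, because the 2 h margin is stated for sensory block duration only.

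The cost is mostly wording, plus extracting the times of in-hospital oral doses from records already collected. The interval is somewhat wider (about 1.24 h against 0.98 h half-width in the illustration), and this secondary outcome loses its formal equivalence conclusion.

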### Data collection plan

Data will be collected according to the Source-CRFs/CRFs. All data collection will be conducted by a research staff member, either a research assistant or a co-investigator, who is blinded to the patient's treatment allocation.

1. Identifying information, exclusion criteria, surgical procedure description and anesthesia data will be collected preoperatively.
2. Procedure details, including: sedative used, procedure duration (end of injection), pain on injection and the presence of blood will be collected during the block procedure.
3. Pinprick sensation in the C4-T1 dermatomes at 10 and 20 minutes post block (to characterize presence/absence of block). Pain Sensation is characterized as a: (2) = sharp sensation, (1) = dull sensation only, or (0) = no sensation.
4. Motor function (elbow flexion for biceps) at 10 and 20 minutes post block. Power is graded using (2) = normal movement, (1) = reduced movement and (0) = no movement.
5. Intra-operative anesthesia data collection. Time of first Incision, administered anesthesia and time procedure ended.
6. Room air pulse oximetry 1 hour after admission to PACU/recovery room (to characterize respiratory function near discharge)
7. Blood Glucose level in PACU.
8. An account of analgesia administered in PACU.
9. Numerical rating scale (NRS) pain scores 1 hour after admission to PACU to PACU/recovery room
10. Information regarding post block complications (including pain and bruising around the block site) will be collected in a 1 week postoperative telephone call with the patient.
11. Time to first pain sensation in the shoulder, analgesic use and return of the affected hand to normal strength will be captured in the take home patient diary and reported at follow-up telephone calls.
12. NRS pain scores, analgesia consumption and side effects experienced will be captured at: 12hours/bed time, 24 hours and 7 days post-operatively in the patient's diary reported at follow-up telephone calls.

Upon achieving enrolment of the specified 180 patients and data is collected, the database will be verified, and analyzed by the biostatistician.

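### Repeated measures ANOVA for opioid consumption and NRS has no missing-data rule, sphericity correction or target contrast; a mixed model with an arm difference at each time would be better

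*Combined protocol and SAP*

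**What the plan says.** Section E.vii (Statistical analysis) gives one clause on these outcomes: "Continuous secondary outcomes (opioid consumption, NRS) will be assessed with repeated measures ANOVA". It does not say whether the result is the group effect or the group-by-time effect, whether sphericity will be checked or corrected for, or how patients with missing values will be handled.

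The measurement times are in section E.v (Secondary Outcomes): "NRS for pain at 12hrs/Bed time (if patient retires to bed before the 12hr time point), 24hours, 7 days", and for opioids "Opioid consumption on POD 1 at 12 hours/bed time if patient retires to bed before the 12hr time point), 24 hours and 7 days". That list does not say whether opioid use is an interval amount or a running total. Section E.iii (Protocol) does describe the recording: "Postoperatively patients will be requested to document interval oral analgesic consumption".

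The values are self-reported. Item 12 of the Data collection plan has them captured at "12hours/bed time, 24 hours and 7 days post-operatively in the patient's diary reported at follow-up telephone calls". Section E.iii schedules the calls for postoperative days 1 and 7 and lets them move by up to 5 days.

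The only provision for incomplete data is in section E.vi (Sample size calculation). It begins "To account for incomplete data or loss to follow-up" and raises recruitment from 174 to 180. It is part of the primary-outcome calculation.

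**The concern.** Three things are left open, and each can affect what is reported for pain and opioid use.

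- **Missing values.** Classical repeated measures ANOVA needs all three values from each patient. Gaps are foreseeable in a home diary read out by telephone. Leaving out partly observed patients loses precision. If gaps depend on pain already recorded, it can also bias the comparison.
- **Sphericity.** The within-patient tests assume equal variances of the differences between times. The gaps here are 12 hours and then 6 days, so this is unlikely to hold.
- **Target contrast.** The assessments fall in the first evening, at 24 h and at day 7. A group effect averaged over them can dilute a difference that exists at only one time. Because the plan does not name the test that counts, that choice can be made after the data are seen.

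**Working it through.** **1. The plan's own figure.** No sample size is given for these outcomes. The primary figure reproduces as two one-sided tests with margin 2 h, SD 4 h, true difference 0, 0.05 per side and power 0.9:

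n = 2 × [4 × (1.645 + 1.645) / 2]² = 86.58, rounded up to 87 per group (174 total).

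Recruiting 180 leaves 6 spare patients, and 6/180 = 3.3%.

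**2. Complete-case loss.** The documents give no missing-data rate, so p, the proportion missing at each time, is assumed. With independent gaps the loss is 1 − (1 − p)³. If the same patients miss every time, it is p.

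| p | Loss, independent | Kept of 180 | Loss, same patients | Kept of 180 |
|---|---|---|---|---|
| 3% | 1 − 0.97³ = 8.7% | 164 | 3% | 175 |
| 5% | 1 − 0.95³ = 14.3% | 154 | 5% | 171 |
| 10% | 1 − 0.90³ = 27.1% | 131 | 10% | 162 |

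An intermediate case is two independently missed calls, with the 12 h and 24 h values lost together. The loss is then 1 − (1 − p)², or 5.9%, 9.8% and 19.0%. For scale, independent missingness of 1 − (174/180)^(1/3) = 1.1% per time already takes complete cases below 174.

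**3. Sphericity.** The ANOVA with 2 groups and 3 times was simulated with no group difference, 90 per group, 10,000 runs per pattern and nominal level 5%. The documents give no variances or correlations, so all patterns are assumed. Correlations are in the order 12 h with 24 h, 12 h with 7 days, 24 h with 7 days.

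| SDs | Correlations | Epsilon | Group-by-time, uncorrected | With Greenhouse-Geisser |
|---|---|---|---|---|
| 1, 1, 1 | 0.5, 0.5, 0.5 | 1.00 | 5.2% | 5.2% |
| 3, 2.5, 2 | 0.5, 0.2, 0.3 | 0.94 | 5.3% | 5.0% |
| 1, 1, 1 | 0.6, 0.2, 0.2 | 0.86 | 5.7% | 5.0% |
| 1, 1, 1 | 0.7, 0.05, 0.05 | 0.74 | 6.2% | 4.9% |
| 1, 1, 3 | 0.5, 0.3, 0.3 | 0.59 | 7.3% | 4.9% |
| 1, 1.7, 6 | 0.8, 0.4, 0.5 | 0.53 | 7.8% | 4.7% |

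The group main effect stayed at 4.6% to 4.8% throughout. The Monte Carlo standard error is 0.2 to 0.3 points. With three times epsilon cannot fall below 0.5, so the last row is near the limit. That row mimics running totals; the row above it mimics interval amounts.

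**4. Dilution by averaging.** Assume a difference of 0.5 SD at 24 h only, equal SDs, between-time correlation 0.5, 90 per group and two-sided 5%.

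- Tested at 24 h: SE = √(2/90) = 0.149 SD; 0.5/0.149 = 3.35; power = Φ(3.35 − 1.96) = 92%.
- Tested as the average: the difference is 0.5/3 = 0.167; SE = √[(1 + 2 × 0.5)/3] × 0.149 = 0.122; ratio 1.37; power = Φ(1.37 − 1.96) = 28%. Correlations of 0.7 and 0.3 give 24% and 33%.
- Tested as group-by-time: noncentrality = 90 × 2 × ¼ × (1/6) / (1 − 0.5) = 15 on 2 and 356 degrees of freedom; power about 94%.

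So whether this difference is found depends on which of the ANOVA's tests is taken as the result.

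**The case against.** The strongest reply is that a short method name is being read as a set of defects. Much of that reply stands.

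- **A reader might infer that the plan deletes incomplete patients.** It states no such rule. Deletion is the usual behaviour of the classical method, and the name is sometimes used loosely for a mixed model.
- **Independent gaps may be too pessimistic.** Values reach the trial through two calls, so gaps may cluster. If the same patients miss every time, the loss is only p and a mixed model recovers nothing for them.
- **A reader might infer that the group comparison is invalid.** Sphericity does not touch the group main effect, and a Greenhouse-Geisser correction brings the group-by-time test back to about 5%. The plan specifies no correction, however.
- **A reader might infer that unequal variances follow from the planning values.** With mean 18 h and SD 4 h, about 7% of blocks would have ended by 12 h and 93% by 24 h. These proportions are symmetric: 0.067 × 0.933 = 0.062 at both times. They say nothing about variances of differences in NRS or opioid use.
- **A reader might infer that the opioid totals contain one another.** The documents do not establish this, because section E.iii has patients record interval amounts. The secondary-outcome list is merely silent.
- **A reader might infer that ANOVA must miss a difference at one time.** Its group-by-time test can find one, as step 4 shows. The fault is that no contrast is named.

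What remains is a classical method that needs complete data, with no missing-data rule, no correction and no stated contrast.

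**Conclusion.** The point holds at a limited size. For two secondary outcomes the plan names a method that, in its classical form, uses only patients with all three diary values, and it leaves the missing-data rule, the sphericity correction and the target contrast unstated. The loss is about 9%, 14% or 27% under independent gaps and about 3%, 5% or 10% under fully clustered gaps, for assumed missingness of 3%, 5% or 10% per time. The true figure probably lies between. The uncorrected group-by-time test may run to about 7% to 8% Type I error in the more extreme assumed patterns. That sphericity fails is an expectation from the spacing, not something the documents show.

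A reader should not carry this over to the main result: the primary equivalence test and the sample size of 87 per group are unaffected.

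**What to change.** In section E.vii, replace repeated measures ANOVA with a linear mixed model fitted to all available values. Include arm, time as a category, arm-by-time and site (randomization is stratified by site, section E.iii), with unstructured covariance within patient. Report the arm difference with its 95% CI at each of the three times as the stated result, and state the missing-at-random assumption.

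In section E.v, define opioid consumption by the non-overlapping intervals that the diary can already supply: 0 to 12 h or bedtime, from there to 24 h, and from 24 h to 7 days. Add a rank-based or bootstrap check for skew.

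The cost is SAP wording and slightly more programming, with no extra patients or data. The model does not remove bias if gaps depend on pain that was never recorded, and it adds nothing for patients with no diary values at all.

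### Repeated measures ANOVA of opioid consumption over windows of about 12 h, 12 h and 6 days dilutes a first-day difference between routes; a separate 0-24 h comparison should be specified

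*Combined protocol and SAP*

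**What the plan says.** - **Method (E.vii, Statistical analysis):** "Continuous secondary outcomes (opioid consumption, NRS) will be assessed with repeated measures ANOVA". The section does not say which effect tests the route (group or group by time), whether the form is univariate or multivariate, what scale or transformation is used, or whether there is a comparison at any single time.
- **Outcome (E.v, Secondary Outcomes):** "Opioid consumption on POD 1 at 12 hours/bed time if patient retires to bed before the 12hr time point), 24 hours and 7 days".
- **Recording (E.iii, Protocol):** "Postoperatively patients will be requested to document interval oral analgesic consumption". Doses "will be converted into equianalgesic doses (oral morphine equivalents"), with no scaling per hour or per day.
- **Capture (Data collection plan, item 12):** "NRS pain scores, analgesia consumption and side effects experienced will be captured at: 12hours/bed time, 24 hours and 7 days post-operatively".
- **Calls (E.iii):** the day 1 and day 7 calls may move by "up to 5 days depending on patient availability".
- **Expected block duration (E.vi):** for the plain block, "we expect mean sensory block duration of 12 hours with a standard deviation of 4 hours"; with perineural dexamethasone, a prolongation of "approximately 50% thereby increasing block duration to 18 hours".

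The plan gives no expected amount, SD, correlation or power for opioid consumption.

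**The concern.** A pain score is a reading at one moment, and averaging it over three times makes sense. Opioid consumption is an amount that builds up over a window. E.vii gives both the same method. If the diary entries are interval amounts, the third window is about 12 times as long as each of the first two, and an unweighted average over the three entries is governed by whatever happens after the first day.

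The routes are most likely to differ in opioid need while the blocks are wearing off. On the plan's own durations that is mostly within 24 h. An analysis dominated by days 2 to 7 could return a non-significant result when one route needs more opioid on the first night, and a reader could take that result as support for similar analgesia.

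**Working it through.** **1. The plan's own figure.** The only sample size stated is for the primary outcome. Two one-sided tests at 0.05, SD 4 h, margin 2 h, true difference 0, power 0.90:

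n = 2 × [4 × (1.645 + 1.645) / 2]² = 86.6, so 87 per group.

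This matches E.vi. It gives no information on the precision of opioid consumption. The recruitment target of 90 per group is used below.

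**2. What the between-route test compares.** In a balanced repeated measures ANOVA, the group effect is a two-sample t-test on each patient's unweighted mean of the entries. With interval amounts a (0-12 h), b (12-24 h) and c (24 h-7 d), that mean is (a + b + c)/3, one third of the 7-day total. The t statistic does not change with scale, so the test is the t-test on 7-day consumption. This needs no assumed SD, and it holds with complete data and with any sphericity correction. With cumulative entries the mean is (3a + 2b + c)/3, which gives the early windows more weight.

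**3. When the blocks end.** Normal model, SD 4 h (stated for the plain block and carried over to 18 h by assumption):

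- mean 18 h: P(end before 24 h) = Φ((24 − 18)/4) = Φ(1.5) = 0.933
- mean 12 h: Φ((24 − 12)/4) = Φ(3) = 0.999

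**4. Size of the loss in an assumed scenario.** Interval SDs are 8, 12 and 40-80 mg oral morphine equivalent, with correlation ρ between windows of 0.3-0.5. The route difference is +2.1, +7.0 and 0 mg, or 9.1 mg in all. That is two 30 mg codeine tablets at the protocol's ratio (60/6.6 = 9.1). The comparison uses 90 per arm, two-sided 0.05, noncentral t, and SE = SD × √(2/90).

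| Test | Difference | SD | Power |
|---|---|---|---|
| Direct 0-24 h total, a + b, ρ 0.3 | 9.1 | √(64 + 144 + 0.6×96) = 16.3 | 0.96 |
| Same, ρ 0.5 | 9.1 | √(208 + 96) = 17.4 | 0.94 |
| Between-route, interval, a + b + c, late SD 40, ρ 0.3 | 9.1 | √(265.6 + 1600 + 480) = 48.4 | 0.24 |
| Same, late SD 80, ρ 0.5 | 9.1 | √(304 + 6400 + 1600) = 91.1 | 0.10 |
| Between-route, cumulative, 3a + 2b + c, late SD 40, ρ 0.3 | 20.3 | √(2752 + 1497.6) = 65.2 | 0.55 |
| Same, late SD 80, ρ 0.5 | 20.3 | √(7552 + 4416) = 109.4 | 0.24 |

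Simulation with skewed (gamma) amounts gave 0.92-0.97 for the direct comparison, 0.08-0.24 for interval amounts and 0.22-0.56 for cumulative amounts.

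**5. Dependence on the late-window SD.** A second set of assumptions used 87 per group and a first-day effect of 0.5 SD of the 0-24 h total, split evenly over the two early windows. The direct comparison has power 0.91. The between-route test gives:

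| SD ratio of the windows | Interval | Cumulative |
|---|---|---|
| 1:1:12 | 0.07 | 0.15-0.16 |
| 1:1:6 | 0.12-0.13 | 0.33-0.38 |
| 1:1:3.46 | 0.23-0.24 | 0.51-0.64 |
| 1:1:2 | 0.39-0.47 | 0.67-0.80 |
| 1:1:1 | 0.62-0.76 | 0.80-0.87 |

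Power is below the direct comparison in every row, but the loss runs from severe to slight.

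**6. The route-by-time test.** In the step 4 scenario the Greenhouse-Geisser form had simulated power of 0.06-0.17. The multivariate form reached 0.63-0.82 on interval amounts and 0.96-0.98 on cumulative amounts. With the even split of step 5 and SD ratios of 3.46 or more, the multivariate form had 0.07-0.13 on interval amounts and 0.70-0.85 on cumulative amounts. Whether it recovers the loss therefore depends on how the difference divides between the two early windows and on how entries are recorded.

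**The case against.** The strongest reply is that the plan says only repeated measures ANOVA. It does not commit to the group main effect. A multivariate route-by-time test or a comparison at 24 h is compatible with the wording and could find a first-day difference. That stands. A reader might infer that the planned method must swamp any early difference, and the documents do not support so strong a claim. They also do not specify any test that would avoid the loss.

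The windows are not firmly defined. The word interval appears once, in the diary instruction, while E.v and the data collection plan give amounts at time points. Cumulative entries are possible, and so is use on day 7 alone, in which case the windows would not differ greatly. This limits the conclusion to a conditional one and is itself a gap to close.

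The opioid SDs, correlations and true difference are all assumed. With a late-window SD no more than twice the early ones, dilution is a fair description and swamping is not.

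Three further inferences go beyond the text:

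- Nothing ranks opioid amount as the main support for equivalence. It is one of nine secondary outcomes. Time to first opioid is listed separately, and pain scores are collected at 12 h and 24 h. Neither of these measures how much opioid each route needs.
- No passage says that opioid use cannot differ between routes once the block has ended. The 93% figure shows where most blocks end, and no more than that.
- The plan does not propose to read a non-significant opioid result as equivalence. Its background section criticises a previous trial for that reasoning.

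**Conclusion.** The concern holds in conditional form. If the entries are interval amounts, the between-route test is a test of 7-day consumption. That part is algebra and needs no assumed SD. A difference confined to the first 24 h is then diluted. For a 9.1 mg first-day difference with 90 per arm and SDs of 8, 12 and 40-80 mg, power falls from about 95% to about 10-25% on interval amounts, or 22-56% on cumulative amounts. These figures rest on assumed SDs and correlations, and the loss shrinks as the late-window SD shrinks. A multivariate route-by-time test recovers much of it in that scenario, but the plan does not specify one and the recovery is not assured under other splits of the difference. This is a worthwhile, inexpensive improvement to one secondary outcome and has no bearing on the primary analysis or the 87 per group.

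**What to change.** In E.vii:

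1. Take opioid consumption out of the repeated measures ANOVA. Pain scores are not affected by this point.
2. State that the entries are interval amounts, and give the start and end of each window. Say how the last window closes if the day 7 call is moved.
3. Compare the 0-24 h oral morphine equivalent total between routes as one value per patient: mean difference with 95% CI, and a bootstrap or log(x + 1) analysis as a check for skew. The total is the sum of the first two entries if they are interval amounts, or the 24 h entry alone if they are cumulative; summing cumulative entries would count the first 12 h twice.
4. State whether recovery-room opioid, which is recorded separately, is part of that total.
5. Report the 24 h to 7 day amount as a separate comparison.
6. State that a non-significant opioid result is not evidence of equivalence.

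The cost is a few sentences and two opioid comparisons in place of one omnibus test. No new data are needed.
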